5. STUDY PROCEDURES

5.1 Overview

Participants will complete a total of three assessments before, immediately after, and 3 months following an 8-week period where they will either receive an 8-week series of psychosocial intervention or attention control visits. This equals a total of 11 visits with VUMC. Based on attrition rates from investigations in similar chronic pain conditions,³⁸ we will assume a conservative study dropout rate of 30%, and will recruit up to 96 participants in order to attain complete data on 75 subjects. In order to recruit 96 participants including follow-up we anticipate this study will occur over the course of three to four years. Below we detail a summary of the visit structure along with a figure indicating study flow.

The assessments corresponding to the study will occur in two stages at each of the three timepoints: (1) completion of patient-reported outcomes online, and optional (2) completion of psychophysical testing and the collection of biological samples in person at the CRC. Participants will have the option of enrolling in the first or both stages of these assessment visits, each of which will have separate consent forms.

Once patients pass the phone screen, they will be scheduled for a Study Enrollment visit, to take place remotely over the phone or online. They will present for a remote assessment visit to complete consenting procedures and will be sent patient-reported outcome measures online via REDCap. Those who elected to participate in in-person psychophysical testing procedures will then be scheduled for the CRC. Patients in the Study Enrollment Visit will complete separate consent forms corresponding to the online and in-person study procedures. The eligibility checklist will be reviewed again to ensure participants meet criteria and assessment battery will be given. Participants who enroll in the study will be randomized after the assessment (see section 5.3 for full description of randomization procedures).

Pretreatment visit (1, T0):

Once patients are screened and determined to be eligible to participate in the study, they will complete informed consent and an assessment battery remotely. If they agree to undergo psychophysical testing, they will be scheduled to do so at the **Clinical Research Center** (CRC) for their first pre-treatment assessment visit (procedures detailed below).

Visits (2-9, T1):

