Participants will either receive a series of 8-week psychosocial intervention or attention control visits for an 8-week period at the Osher Center for Integrative Medicine, online, or via telephone. Each of the 8 treatment condition appointments will span 50 minutes.

Post-treatment Visit (10, T2):

Participants will complete a repeat corresponding battery of psychological (stage 1), psychophysical, and biological testing (stage 2) immediately after 8 weeks of visits.

[figure not shown]
3-month Follow-up Visit (11, T3):

Participants will complete a repeat battery of testing to investigate effects at follow-up.

5.1.1 Visit schedule adjustments due to infection precautions:

If circumstances arise where individuals cannot attend assessment visits in-person (e.g. due to system-wide precautions related to infection control), participants will engage in screening and assessment procedures remotely as applicable. Participants electing to participate in Stage 2 of the assessment process will then be invited at a later date to return on site to complete in-person assessment visits as timing and infection control procedures permit.

Figure 1: Study Flow

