5.3 Randomization procedures

Patients will be randomized to the psychosocial self-management group (SM) or attentional control (AC) group after their first assessment visit. Randomization will occur at a 2:1 rate favoring our treatment condition, which will increase power in planned subgroup analyses. Randomization will be unblinded and occur through stratified permuted block methods using randomly-assigned variable blocks (2, 4, and 6). Participants will be stratified by opioid use levels, with those who take opioids more than 3 days per week defined as “regularly using opioids.” Randomization will occur following participants’ study enrollment visit and online assessment completion (Stage 1 assessment) to avoid any selection bias and to ensure adequate balance between treatment groups throughout the study accrual period. These procedures will be conducted by a study biostatistician so that the blocking factor is not known to the study PI or enrollment team to guard against any further selection bias.

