MBM-II⁴⁹: The Michigan Body Map-II (MBM-II) is a self-report measure used to assess the location(s) of chronic pain complaints and widespread body pain. It is a two-sided body image with check-box responses for 35 potential body areas where chronic pain (defined as pain > 3 months) might exist, and a box for “no chronic pain.” It takes 2-3 minutes to complete. In this study, the measure is being used as an indication of centralized pain and pain sensitivity. We will use an open source version of the body map created in Redcap for the Collaborative Health Outcomes Information Registry initiative.

Comorbidity

FS⁵⁰: the Fibromyalgia Symptom Scale is a 7-item questionnaire assessing modified 2010 American College of Rheumatology diagnostic criteria for fibromyalgia and includes a) an index of widespread pain and b) an index of symptom severity via patient self-report. This survey was designed by experts for epidemiologic study. It is administered with a pain body map. A total score on this scale ranges from 0-31, with scores ≥ 13 indicating a high likelihood of fibromyalgia. This scale takes approximately 3 minutes to complete.

MISCI⁵¹: The Multidimensional Inventory of Subjective Cognitive Impairment (MISCI) is a 10-item self-report measure assessing cognitive difficulties in fibromyalgia patients. Items address the past seven days and exist on a Likert scale of 1 to 5, with 5 indicating higher levels of cognitive impairment. The internal reliability and convergent validity of the item are dependable. The MISCI takes <1 minute to complete.

Quality of Life

FSFI⁵²: The Female Sexual Function Index (FSFI) is a 19-item questionnaire with six domains of female sexual functioning. It takes <2 minutes to complete.

IIEF^{53, 54}: The International Index of Erectile Dysfunction (IIEF) consists of 15 items and five domains pertinent to male sexual functioning. It has been studied in varied cultural contexts and translated into 10 languages. The item is reliable and valid, detecting clinical changes well. It takes <2 minutes to complete.

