■ will examine changes in secondary outcomes of interest, including pre- to post-treatment changes in emotional distress (e.g. PHQ-8, GAD-7, PCL-5, CSQ), quality of life and wellness (e.g. PROMIS-29), widespread pain (MBM/Choir bodymap), and perceived treatment benefit (PGI) using similar approaches: linear models for continuous outcomes, proportional odds models for ordinal outcomes, and logistic models for binary outcomes. As ■ training in data analysis progresses, ■ will apply more sophisticated approaches, such as hierarchical modeling. As ■ anticipate potential confounding from factors such as age and time since diagnosis, we will account for these as covariates in the analyses. Further, as opiate use is associated with increased pain sensitivity and decreased pain thresholds on psychophysical testing,⁷³ ■ will stratify groups by opiate use during randomization. ■ will additionally consider opiate use as a covariate in the analyses. To address sex as biologic variable, we will examine sex as a moderator of treatment effects, since men and women perceive pain differently in self-report⁷⁴ and sensory testing.⁸¹

Aim 3: To determine whether patient phenotype moderates treatment response to a SM intervention. As an exploratory aim, ■ will assess the hypotheses that a) higher pre-treatment psychological distress, b) higher baseline temporal summation, and c) number of chronic overlapping pain conditions will be associated with greater SM treatment efficacy. To avoid loss of power from testing a phenotype x treatment x time interaction, ■ will model the change in GUPI and treatment response (PGI) using a proportional odds model adjusted for baseline GUPI, and test for a treatment x phenotype interaction. A positive finding would suggest treatment effects depend on these moderating factors. ■ increased our sample size for this analysis by applying a 2:1 randomization scheme; however, given that our treatment group still constitutes a small sample size (n=50), ■ will set a threshold of p<.2 for the interaction before proceeding with a responder or mediation analysis. ■ will use these analyses to identify factors needing consideration in future studies expanding the generalizability of SM.

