MBM-II ⁴⁹ (with CHOIR bodymap)	Pain experiencing	Widespread pain. Indication via check marks of which body regions experience chronic pain.	1			x		x		x
Fibromyalgia Symptom (FS) scale ⁵⁰ /ACR FM diagnostic criteria	Quality of life	Symptom severity scale. Subscales: Widespread Pain Index (WPI)-check marks for pain areas, Symptom Severity Score (SS)- half is 4-point Likert scale, half is symptom checklist. Used with CHOIR bodymap to determine presence of fibromyalgia.	6			x		x		x
PISES ⁵⁵	Quality of life	Sexual pain, fear, and dysfunction. Subscales: self-efficacy for sexual function, self-efficacy for controlling other	25			x		x		x

		symptoms, self-efficacy for controlling pain during intercourse.							
PROMIS-29 Scale ^{56,57} (without anxiety and depression scales)	Quality of life	Pain, fatigue, function, and physical and emotional health. Likert scale from 1-5 for all but last subscale (0-10). Anxiety and depression subscales omitted. Subscales : physical function, fatigue, sleep disturbance, ability to participate in social roles and activities, pain interference, pain intensity.	29		x		x		x
PCL-5 with Criterion A ⁶⁰	Affective vulnerability	Post-traumatic stress. Parts: traumatic events checklist, questions about worst event, PTSD checklist with a 5-point Likert scale.	25		x		x		x
THQ (baseline only) ⁶¹	Environmental/Social	Trauma exposure and PTSD assessment; used in conjunction w/ PCL to evaluate for trauma. Domains include: crime-related events, general disaster and trauma, physical and sexual experiences.	6, 7		x				
CSQ-CAT ⁶³	Beliefs and Attitudes	Catastrophizing measure, 7-pt Likert scale.	6		x		x		x
PGI-C ⁶⁴	Treatment response	Perceived response to treatment, 7-pt Likert scale.	1				x		x
Patient Reminder Script	Reminder	Give patient info on upcoming visit.	N/A	x		x		x	
MISCI ⁵¹	Cognition	Cognitive dysfunction associated with widespread pain. 5-pt Likert scale. Domains: mental clarity, memory, attention/concentration, executive functioning, language.	10		x		x		x
GAD-7 ⁵⁹	Affective vulnerability	Assessment of anxiety, 4-pt Likert scale.	7		x		x		x

RICE ⁴⁸	Screening	Surrogate for diagnosis in patients outside of system. 11 items.		x							
FSFI ⁵² , IIEF ^{53,54}	Quality of life	Sexual dysfunction - F/M. FSFI subscales: desire, arousal, lubrication, orgasm, sexual satisfaction, pain. Likert scale. IIEF domains: erectile function, orgasmic function, sexual desire, intercourse satisfaction, overall satisfaction. Likert scale.	19, 15		x		x		x		

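### The body map needs more than 3 months of pain but is analysed as an 8-week change, so on the planned schedule it can show sites resolving but not spread that begins during treatment

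*Combined protocol and SAP*

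**What the plan says.** Section 5.7.1 (MBM-II) presents a two-sided body image with boxes for "35 potential body areas where chronic pain (defined as pain > 3 months) might exist", plus a box for no chronic pain. It gives the map's role in this study as a marker of centralised pain and pain sensitivity. The trial uses an open-source REDCap version built for the CHOIR registry; the instruction shown to participants on that form is not reproduced.

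The protocol table (Appendix O) describes the item as "Indication via check marks of which body regions experience chronic pain". It schedules the map at pre-treatment, post-treatment and the 3-month follow-up, with no different time frame for repeat use.

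Section 9.1 (Aim 2) introduces the secondary outcomes as "including pre- to post-treatment changes in emotional distress" and carries the list on to "widespread pain (MBM/Choir bodymap), and perceived treatment benefit (PGI) using similar approaches".

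Section 5.1 sets "three assessments before, immediately after, and 3 months following an 8-week period", with the post-treatment battery given "immediately after 8 weeks of visits". Section 5.3 randomises after the online baseline assessment. Neither section gives a maximum gap before the first session or a window for the post-treatment visit.

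**The concern.** The duration a body area needs before it counts is longer than the interval over which change is measured. Two things follow. An area that becomes painful during treatment is too recent to be marked at post-treatment. An area whose pain was already present but too recent at baseline can pass the threshold by post-treatment and look like a new site.

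The other repeated measures with a stated look-back in section 5.7.1 do not have this problem: MISCI uses seven days, PHQ-8 two weeks and PCL-5 the past month, all shorter than 8 weeks.

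Widespread pain is a named secondary outcome, and the Background ties it to worse severity, distress and sleep and to a theorised benefit from self-management. If the map is read as a general measure of change, an added site may be taken as on-treatment worsening when its onset came before randomisation. The absence of added sites may be taken as prevented spread when spread could not have been recorded.

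**Working it through.** **Inputs.** Threshold: more than 3 months (section 5.7.1). Treatment period: 8 weeks = 56 days (section 5.1). Follow-up: 3 months after that (section 5.1). Randomisation: after the baseline questionnaires (section 5.3). Day 0 is baseline and randomisation. The gap to session 1 is not stated, so I start from zero and then vary it.

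**Check against the plan's own figure.** One month = 365.25/12 = 30.44 days, so 3 months = 91.3 days. Then 56 + 91.3 = 147.3 days, and 147.3/30.44 = 4.84 months. This agrees with the 5 months of participation stated in the recruitment scripts.

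**Latest onset countable at post-treatment.** 56 − 91 = day −35. Pain starting on day 0 has lasted 56 days (1.84 months) and is about 35 days (5 weeks) short. No onset after randomisation qualifies.

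**Pre-baseline pain that ages into a new site at post-treatment.** An area is uncounted at baseline if its pain began after day −91. It is countable at post-treatment if the pain began by day −35 and persists. The window runs from day −91 to day −35: 91 − 35 = 56 days of onset dates.

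**Sensitivity to slippage.** The countable window for post-randomisation onsets is max(0, 56 + slippage − threshold).

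| Total slippage (days) | Randomisation to post-treatment (days) | Window, threshold 91 days | Window, threshold 84 days (12 weeks) |
|---|---|---|---|
| 0 | 56 | 0 | 0 |
| 28 | 84 | 0 | 0 |
| 35 | 91 | 0 | 7 |
| 42 | 98 | about 7 | 14 |

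The window is empty up to about 5 weeks of slippage (4 weeks if 3 months is read as 12 weeks) and only days wide just beyond that.

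**The same sums at the 3-month follow-up.** Latest countable onset: 147 − 91 = day 56, which covers the treatment period. Onsets from day 56 to day 147 are still missed. Every persisting onset from day −91 to day 0 can now appear as a new site: 91 days, against 56 at post-treatment (91/56 = 1.6, about 60% wider).

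**The case against.** The strongest points on the other side are these.

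- **The on-screen wording is unknown.** The CHOIR form may ask about current pain, and Appendix O says chronic pain without a duration. This stands as a limit. The only definition in the documents is the one in section 5.7.1, though, and if the form differs, that section needs correcting.
- **The schedule is not fixed.** No gap or visit window is stated, and participants may tick shorter pain despite the instruction. This also stands: the result is conditional on the planned schedule and on the definition being followed.
- **The hypothesis is improvement, and improvement remains visible.** A resolved area can be unticked. This stands, although the text does not say how long an area must be pain-free first.
- **The consequence is modest.** It is one of several secondary outcomes in a pilot aim. Pain is also captured by the GUPI pain subscale and the PROMIS pain items, and the map's use as a baseline phenotype marker is unharmed. The documents give no rate of new pain areas over 8 weeks, so the lost sensitivity cannot be sized.

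A reader might infer that a finding of no worsening is built in. It is not: the count can rise at post-treatment through ageing of pre-baseline pain. What is lost is the ability to attribute a rise, or its absence, to the treatment period.

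A reader might also infer that moving the analysis to follow-up cures the problem. It does make on-treatment onsets countable, but it enlarges the ageing artefact and leaves later onsets uncounted.

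**Conclusion.** The point holds, with minor to moderate weight. On the planned schedule, with total slippage under about 5 weeks and the definition in section 5.7.1 applied as written, the post-treatment change in the body map can show resolution of baseline sites. It cannot show or rule out spread that begins during treatment, and pain that began about 35 to 91 days before baseline can appear as a new site although nothing changed.

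The documents do not support reading this as a bias between the arms. The same instrument and timing apply to both randomised groups, so the loss is in sensitivity and interpretability. The GUPI primary analysis and the sample size do not depend on it.

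Nor do they establish that the Fibromyalgia Symptom scale is affected. It is given with a body map, but the documents do not say that its widespread-pain index is scored from the more-than-3-month boxes, and section 9.1 does not name it as an outcome.

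**What to change.** 1. Check the instruction on the REDCap/CHOIR map. If it already asks about current pain, correct section 5.7.1 to say so; the problem then disappears.
2. If it uses more than 3 months, give participants not yet assessed at baseline the same current or past-week instruction at all three visits for the change outcome, and keep the more-than-3-month map at baseline for phenotyping. The cost is a second baseline map (2 to 3 minutes by the protocol's own estimate), a modified instruction, and a change outcome available only for later participants.
3. For participants already enrolled, define the post-treatment outcome in section 9.1 as resolution of areas marked at baseline, and state that no conclusion about new or prevented spread will be drawn from it. The cost is a sentence or two and a narrower conclusion.
4. Follow-up map results may be reported in addition, since onsets up to about day 56 become countable there. They should not simply replace the post-treatment analysis, and the report should state the 91-day ageing window and the onsets still missed after about day 56. The map is already scheduled at that visit, so no new data collection is needed.

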5.7.2 Psychophysical (QST) measures (applies to the second assessment stage only)

Psychophysical testing applies different types of stimuli, such as pressure or heat, to measure central sensitization and pain responsiveness in the body.⁶⁵ In this investigation, psychophysical testing methods will replicate protocols currently used by mentors (██████████)⁶⁶⁻⁶⁹ and include the following elements: 1) an evaluation of temporal summation (as a biomarker for central sensitization⁷⁰, 2) thermal pain threshold and tolerance, and 3) pressure pain threshold. These methods are validated, replicable, and widely used in the pain field to index central sensitization, including in ongoing studies examining pelvic pain, and pain phenotypes.^{39,71-73} In replication, we will use a Medoc TSAII NeuroSensory Analyzer with a 9-cm² peltier thermode delivering a controlled heat stimulus able to rapidly return to baseline temperature by active cooling (at 10°C/second). We will assess temporal summation using software provided with the unit that administers a standardized oscillating thermal stimulation protocol designed specifically to elicit C-fiber mediated temporal summation.⁶⁶⁻⁶⁸ We will evaluate temporal summation on the forearm at two target temperatures (47°C and 49°C), by applying a sequence of 10 heat pulses in a fixed position at each target temperature. These pulses (each 0.5 seconds) begin at 40°C and increase to the target temperature with rapid return to baseline at 0.4 Hz, a frequency known to elicit C-fiber mediated wind-up in the dorsal horn.⁷⁴ In each sequence, immediately after each heat pulse, subjects provide a verbal numeric pain intensity rating on a 0–100 scale (0 = “No Pain or Warmth” and 100 = “Worst Possible Pain”). The standardized slope of the line fitted to the series of 10 pulses at each temperature indexes temporal summation and serves as a quantitative marker of central sensitization.⁶⁶ Additional techniques will assess thermal pain threshold and tolerance, and pressure pain threshold as previously described.⁶⁶⁻⁶⁸ Thermal measures involve four pain threshold trials, followed by four pain tolerance trials, with the probe applied to slightly different target sites for each trial to avoid local sensitization. Means for the four threshold and tolerance trials are separately derived. Pressure pain threshold testing³⁹ uses an algometer to assess pain threshold at four sites: the upper fibers of the trapezius, the tibialis anterior, forearm, and pelvic region. This total process takes approximately 30 minutes to complete.

5.7.3 Biological samples to be taken (applies to the second assessment stage only)

Urinalysis (UA): All participants will provide urine samples and undergo a urinalysis (UA) following their assessment visit to assess for the presence of infection. Participants will undergo repeat UA at follow-up visits to assess the potential impact of infection symptoms on pain responding and patient phenotype. Urine samples given will be transferred to a lab in Medical Center North (████), frozen, and undergo urinary microbiome and biomarker analyses at a later date to facilitate patient phenotyping.

Blood samples: Participants will undergo blood draws to obtain serum and plasma for research purposes. These will be obtained at a single timepoint during the assessment visit, prior to sensory testing. As such a trained Registered Nurse of the VUMC Clinical Research Center (CRC) will follow clinic procedures to secure these samples, which will be stored on-site at the CRC. We will use a warm compress beforehand as needed to help facilitate the procedure. We will collect 12cc of blood, using two lavender K2-ETDA 4ml vials for plasma analysis, one 3.5ml yellow top vial aliquot for serum blood collection, and a 2ml vial coated in lipopolysaccharide (LPS) to examine LPS-stimulated cytokines. Study research nurses will spin down serum and plasma samples and place into a cryotube for each patient during the in-person assessment visit. A subset (2ml) of the samples placed in LPS-coated vials will be stimulated in an agitator at 37 degrees for 24 hours, after which the supernatant is isolated with a valve separator accompanying the vial. The isolated supernatant will be placed in cryotubes by CRC nursing staff at 24 hours and frozen at -80 degrees Celsius the following day. Samples will be labeled and stored in the CRC laboratory during data collection. Samples that have yet to be analyzed at the conclusion of data collection will be transferred to a secure, temperature-controlled location under the purview of the PI and study primary mentor [REDACTED] in her laboratory space ([REDACTED] [REDACTED] Samples will be taken to assess for inflammatory biomarkers, including LPS-stimulated cytokines to facilitate patient phenotyping.

Post-treatment and follow-up assessments

Post-treatment and follow-up assessments will occur immediately following the conclusion of the 8-week treatment or control period, and then 3 months following. These visits will occur again in two stages both online and at the CRC (as applicable) and reflect the same process as the pre-treatment assessment, including self-report assessments, psychophysical testing and biological samples taken. Each visit will take approximately 60-90 minutes in total.

Visit schedule adjustments in the event of infection precautions:

If circumstances arise where individuals cannot attend assessment visits in-person (e.g. due to system-wide precautions related to infection control), participants will engage in screening and assessment procedures remotely as applicable. Participants electing to participate in in-person assessment procedures will then be invited at a later date to return on site to complete in-person assessment visits as timing permits.

